5.2.8.1. ACY-1215

Patients must remain on their assigned ACY-1215 dose in Cycle 1 during the dose escalation phase of the study, or be withdrawn from the study. If toxicity attributable to pomalidomide or dexamethasone is seen during Cycle 1, dose reductions may be made as described in Table 6 and Table 8. Patients should receive 80% of planned doses to be evaluable for SRC review.

For toxicities observed that may be attributable to pomalidomide (see Table 6) or dexamethasone (see Table 8), dose reductions should be attempted with these treatments prior to reducing the dose of ACY-1215.

After Cycle 1, patients who are unable to tolerate ACY-1215 treatment may have the dose reduction steps presented in Table 3 until a tolerable dose is achieved.

Table 3 ACY-1215 Dose Modifications

Dose level	Starting dose of ACY-1215	1 st dose reduction	2 nd dose reduction
-2	160 mg QD on Days 1-5, and 8-12	80 mg QD on Days 1-5, and 8-12	NA
-1	160 mg QD on Days 1-5, 8-12, and 15-19	80 mg QD on Days 1-5, 8-12, and 15-19	NA
1	160 mg QD on Days 1-21	80 mg QD on Days 1-21	NA
2	240 mg QD on Days 1-21	160 mg QD on Days 1-21	80 mg QD on Days 1-21
3	160 mg BID on Days 1-21	160 mg QD on Days 1-21	80 mg QD on Days 1-21

Table 4 Dose Modification Instructions for ACY-1215 for Hematologic Toxicities

Toxicity	Dose Modification
Neutropenia (1st occurrence): 
• ANC < 500/μL or febrile neutropenia (fever \geq 38.5°C and ANC < 1,000/μL)• ANC return to \geq 500/μL	Interrupt ACY-1215 treatment, follow CBC weekly. Resume ACY-1215 at one dose level lower than at the time of the first occurrence per Table 3. For the second occurrence of neutropenia (each subsequent drop of ANC < 500, interrupt and follow as above and resume at one dose level below the current dose.
Thrombocytopenia (1st occurrence): 
• Platelets < 25,000/μL• Platelets return to \geq 50,000/μL	Interrupt ACY-1215 treatment, follow CBC weekly. Resume ACY-1215 at one dose level lower than at the time of the first occurrence per Table 3. For the second occurrence of thrombocytopenia (each subsequent drop of platelets < 25,000), interrupt and follow as above. When platelet count returns to 50,000, resume at one dose level below the current dose.

Table 5: Dose Modification Instructions for ACY-1215 for Non-hematologic Toxicities

Toxicity	Dose Modification
Grade 1 or Grade 2	Continue current ACY-1215 dose regimen at the discretion of the investigator.
Grade 3 Non-hematologic ¹	Hold ACY-1215 dose until value(s) return to \leq Grade 2; initiate therapy at one dose level lower than at the time of the first occurrence per Table 3.

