1.1.4.4. Pharmacodynamics

Pharmacodynamic analyses in PBMCs revealed at least a 2-fold increase in acetylated tubulin, the pharmacological marker of HDAC6 inhibition, in all patients at ACY-1215 monotherapy doses of ≥ 160 mg. Additionally, a modest increase in acetylated histones was seen at an ACY-1215 monotherapy dose of 240 mg; at lower dose levels of 40 and 80 mg, 1 and 2 patients, respectively, had a measurable increase in acetylated tubulin in PBMCs.[49]

The data show that exposures observed at ACY-1215 doses ≥ 160 mg are likely to achieve the target change in pharmacodynamic markers and attain drug levels in the range where efficacy was observed in nonclinical studies (see Investigator's Brochure, [47]).

Further information about ACY-1215 can be found in the investigator brochure.

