5.2.8. Dose Modifications

Before each scheduled study drug dose administered in the clinic, the patient will be evaluated for possible DLTs that may have occurred after the previous dose(s) as described in Section 5.2.6. If a toxicity is considered to be related to a particular drug(s), then the dose of the drug(s) to which the toxicity is considered related may be modified per the instructions outlined in Section 5.2.8.1, Section 5.2.8.2, and Section 5.2.8.3. Conversely, if the toxicity is considered unrelated to a particular drug(s), then no modification of that drug(s) is required.

No dose modifications for ACY-1215 are to be performed in Cycle 1. After Cycle 1, patients who are unable to tolerate ACY-1215 treatment may have the dose reduction steps presented below until a tolerable dose is achieved.

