5.2.8.2. Pomalidomide

Toxicities considered related to pomalidomide are to be managed as shown in Table 6 and Table 7.

Table 6 Dose Modification Instructions for Pomalidomide for Hematologic Toxicities

Toxicity	Dose Modification
Neutropenia Grade 4 neutropenia (ANC < 500/ μ L) or Febrile neutropenia (fever \geq 38.5°C and ANC < 1,000/ μ L)	Hold the pomalidomide dose for remainder of cycle. If the patient was not receiving Granulocyte colony-stimulating factor (GCSF) therapy, initiate GCSF therapy at the discretion of the treating physician. On Day 1 of next cycle, continue GCSF as needed and maintain dose of pomalidomide if neutropenia was the only DLT (except during the first cycle for patients enrolled into the MTD segment of the study). Otherwise, decrease pomalidomide by one dose level at start of next cycle. (Note, ANC must be \geq 500/ μ L in the US and Canada and \geq 1,000/ μ L in the EU to restart dosing)
Grade 4 Thrombocytopenia (Platelets < 25,000/ μ L)	Hold the dose for remainder of cycle. Decrease pomalidomide by one dose level when dosing is resumed at next cycle. (Note, platelet count must recover to \geq 50,000/ μ L to restart dosing)

Table 7 Dose Modification Instructions for Pomalidomide for Non-hematologic Toxicities

Toxicity	Dose Modification
Rash = Grade 3	Hold pomalidomide dose for remainder of cycle. Decrease by one dose level when dosing restarted at next cycle (rash must resolve to \leq Grade 1).
Rash = Grade 4 or Blistering	Discontinue pomalidomide dose and discontinue patient from study.
Constipation \geq Grade 3	Hold pomalidomide dose for remainder of cycle. Initiate bowel regimen. Decrease pomalidomide by one dose level when dosing restarted at next cycle (constipation must resolve to \leq Grade 2).
VTE \geq Grade 3	Hold pomalidomide dose for remainder of cycle. Initiate anti-coagulation treatment. Maintain pomalidomide dose level when dosing restarted at next cycle at discretion of treating physician.
Hypo/hyperthyroidism \geq Grade 2	Hold dose for remainder of cycle. Initiate appropriate medical therapy. Maintain dose level when dosing restarted at next cycle at discretion of treating physician.
Peripheral Neuropathy = Grade 3	Hold pomalidomide dose for remainder of cycle. Decrease pomalidomide by one dose level when dosing restarted at next cycle (neuropathy must resolve to \leq Grade 1).
Peripheral Neuropathy = Grade 4	Discontinue pomalidomide and discontinue patient from study.

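### After Cycle 1, when a grade 4 cytopenia or febrile neutropenia is attributed to both ACY-1215 and pomalidomide, Section 5.2.8.1, Table 4 and Table 6 conflict on which drug is reduced first, and nothing ranks them

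*Combined protocol and SAP*

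**What the plan says.** Five pieces of text bear on this.

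- **Sequence rule** (Section 5.2.8.1, repeated in 5.2.6 and the synopsis). For toxicity that may come from pomalidomide (with a pointer to Table 6) or dexamethasone (Table 8), "dose reductions should be attempted with these treatments prior to reducing the dose of ACY-1215".
- **Table 4** (same section). At a first ANC below 500/µL, febrile neutropenia or platelet count below 25,000/µL, ACY-1215 is interrupted. After recovery the instruction is: "Resume ACY-1215 at one dose level lower than at the time of the first occurrence per Table 3". It sets no condition that pomalidomide was reduced beforehand.
- **Table 6** (Section 5.2.8.2). For grade 4 or febrile neutropenia, pomalidomide stops until the next cycle, and the site is then to "maintain dose of pomalidomide if neutropenia was the only DLT", with an exception in brackets for the first cycle of the MTD segment; otherwise it goes down one level. For grade 4 thrombocytopenia the text is "Decrease pomalidomide by one dose level when dosing is resumed at next cycle".
- **Attribution rule** (Section 5.2.8). "the dose of the drug(s) to which the toxicity is considered related may be modified per the instructions outlined" in the drug-specific subsections, whereas "if the toxicity is considered unrelated to a particular drug(s), then no modification of that drug(s) is required".
- **Cycle 1 bar** (Section 5.2.8). ACY-1215 is not modified in Cycle 1.

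**The concern.** The sequence rule sends the reader to Table 6 for the pomalidomide reduction to be tried first. For neutropenia as the only DLT, Table 6 contains no such reduction. Table 4, a few lines below the sequence rule, lowers ACY-1215 at the first event regardless.

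Attribution to both drugs is a realistic case on the protocol's own text. Section 1.1.4.1 reports grade 3 neutropenia at least possibly related to ACY-1215. Section 5.2.6 lists ACY-1215-related grade 4 neutropenia and thrombocytopenia as DLTs, and Table 6 lists the same cytopenias for pomalidomide. The causality scale in Section 6.1.8.4 lets an investigator choose the category *possible* when the link is unknown and no other cause is clear.

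What is at stake is consistency of the regimen after a grade 4 event. One site may lower pomalidomide and keep ACY-1215; another may lower ACY-1215 and keep pomalidomide. Both can claim compliance. The dose-intensity and dose-reduction summaries (Sections 7.6.3 and 7.6.4) and the Phase 2 exposure-response work (Section 3.4) would then partly reflect which paragraph a site read.

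**Working it through.** No power, alpha or sample-size figure is involved. The check sets the rules side by side by attribution, cycle and event.

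**Step 1. Which situations bring both tables into play?**

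| Situation | Table 4 (ACY-1215) | Table 6 (pomalidomide) | Conflict? |
|---|---|---|---|
| Attributed to pomalidomide only | not triggered | applies | no |
| Attributed to ACY-1215 only | applies | not triggered | no |
| Cycle 1, any attribution | reduction barred | may apply | none over ACY-1215 reduction |
| After Cycle 1, attributed to both | applies | applies | see steps 2 and 3 |

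The attribution rule decides which tables are opened. It does not say which prevails when both are open.

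**Step 2. Neutropenia, after Cycle 1, both drugs.**

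- Sequence rule: try a pomalidomide reduction before any ACY-1215 reduction.
- Table 6: keep pomalidomide if neutropenia was the only DLT.
- Table 4: lower ACY-1215 on restart after the first event.

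If Table 6 is followed, the step that the sequence rule wants first does not take place, yet Table 4 orders the ACY-1215 reduction. The three cannot all be met.

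The result depends on what *only DLT* means. Section 5.2.6 defines DLTs as ACY-1215-related events in Cycle 1 and requires grade 4 neutropenia to last more than 5 days. Table 6 is triggered by grade 4 neutropenia of any duration and is used in all cycles.

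- Strict reading: no event after Cycle 1 is a DLT, so the *otherwise* branch applies and pomalidomide goes down one level. The case then becomes the same as thrombocytopenia in step 3.
- Loose reading (any such toxicity): the three-way conflict stands. Section 5.2.8 itself uses the term this way when it asks for a check for DLTs before each clinic dose.

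Some conflict remains on either reading; only its form changes.

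**Step 3. Grade 4 thrombocytopenia, after Cycle 1, both drugs.** Table 6 lowers pomalidomide, in line with the sequence rule. Table 4 still lowers ACY-1215 at the same first event. ACY-1215 may restart once platelets reach 50,000/µL, while pomalidomide waits for the next cycle, so the ACY-1215 reduction can take effect first. This is a conflict of order and timing between Table 4 and the sequence rule. Table 6 adds none.

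**Step 4. What compliant sites could do with the same Phase 2 patient** (ACY-1215 160 mg; Table 3 gives one step, to 80 mg, a cut of (160 − 80)/160 = 50%):

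| Text followed | ACY-1215 | Pomalidomide |
|---|---|---|
| Sequence rule | 160 mg | one level lower |
| Tables 4 and 6, neutropenia, loose *only DLT* | 80 mg | unchanged |
| Tables 4 and 6, neutropenia, strict *only DLT*; or thrombocytopenia | 80 mg | one level lower |

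**The case against.** The strongest reply is that the attribution rule and the Cycle 1 bar already remove most cases, and that the sequence rule stands ahead of Tables 3 and 4 in the same section and can be read as governing them. The language is also permissive: reductions *should* be attempted, doses *may* be modified. For thrombocytopenia this has force: if 5.2.8.1 were declared to prevail over Table 4, the texts could be followed together. But no passage declares it, and Table 4 is worded as an unconditional instruction. For neutropenia on the loose reading, giving the sequence rule priority still leads to a table that offers no reduction. Permissive wording widens the variation between sites and does not supply an order.

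The reply on impact also stands in part. The sequence rule concerns reductions only, so Table 4's interruption of ACY-1215 is not disputed, and no reading leaves a grade 4 event unmanaged. A later reduction does not remove a patient from the efficacy evaluable population. Dose reductions and the AEs behind them are already tabulated (Sections 7.6.4 and 7.6.6). Investigators would differ on attribution even under reconciled wording.

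Three stronger inferences are tempting, and the documents do not support them.

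- *That 80 mg falls outside the active range.* Section 1.1.4.4 says "at lower dose levels of 40 and 80 mg, 1 and 2 patients, respectively, had a measurable increase in acetylated tubulin in PBMCs", without denominators. Section 3.3 calls 160 mg only likely to be biologically relevant, Section 1.1.4.2 includes 40 mg among the monotherapy doses at which stable disease is cited, and Table 3 itself lists 80 mg as a step.
- *That a given number of patients is affected.* An assumed rate of grade 4 cytopenia applied to the 66 evaluable patients would be only a ceiling, because it counts Cycle 1 events and events attributed to one drug.
- *That restarting ACY-1215 while pomalidomide is held contradicts Section 5.2.* That section describes the assigned combination and does not forbid holding the drugs at different times; the notes to Tables 9 and 10 expressly let patients continue without dexamethasone.

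**Conclusion.** The inconsistency is real but narrow. It applies after Cycle 1 to events attributed to both ACY-1215 and pomalidomide. For grade 4 or febrile neutropenia it is a three-way conflict if *only DLT* is read loosely, and one of order and timing if it is read as Section 5.2.6 defines it. For grade 4 thrombocytopenia it is one of order and timing only. A reader might infer that the rules clash for every cytopenia that pomalidomide may have caused; Section 5.2.8 and the Cycle 1 bar rule that out.

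The size per patient is a choice between ACY-1215 160 mg and 80 mg, with pomalidomide unchanged or one level lower. How many patients this touches, and any effect on the response rate, cannot be derived from the documents. The conclusion rests on the text alone and takes no position on which dosing rule is right.

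**What to change.** Reconcile the synopsis, Section 5.2.6, Section 5.2.8.1, Table 4 and Table 6 into one consistent instruction for each event type. State which passage takes precedence when an event is attributed to both drugs. Clarify what *only DLT* in Table 6 means after Cycle 1. The clinical team chooses the rule; the statistical requirement is that every site applies the same one.

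The cost is a wording change through an amendment, with no added visits, patients or analyses. For patients already treated under the present wording, showing first reductions by drug and triggering event within the planned exposure tables would reveal how far practice differed.

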5.2.8.2. Pomalidomide

Toxicities considered related to pomalidomide are to be managed as shown in Table 6 and Table 7.

Table 6 Dose Modification Instructions for Pomalidomide for Hematologic Toxicities

Toxicity	Dose Modification
Neutropenia Grade 4 neutropenia (ANC < 500/ μ L) or Febrile neutropenia (fever \geq 38.5°C and ANC < 1,000/ μ L)	Hold the pomalidomide dose for remainder of cycle. If the patient was not receiving Granulocyte colony-stimulating factor (GCSF) therapy, initiate GCSF therapy at the discretion of the treating physician. On Day 1 of next cycle, continue GCSF as needed and maintain dose of pomalidomide if neutropenia was the only DLT (except during the first cycle for patients enrolled into the MTD segment of the study). Otherwise, decrease pomalidomide by one dose level at start of next cycle. (Note, ANC must be \geq 500/ μ L in the US and Canada and \geq 1,000/ μ L in the EU to restart dosing)
Grade 4 Thrombocytopenia (Platelets < 25,000/ μ L)	Hold the dose for remainder of cycle. Decrease pomalidomide by one dose level when dosing is resumed at next cycle. (Note, platelet count must recover to \geq 50,000/ μ L to restart dosing)

Table 7 Dose Modification Instructions for Pomalidomide for Non-hematologic Toxicities

Toxicity	Dose Modification
Rash = Grade 3	Hold pomalidomide dose for remainder of cycle. Decrease by one dose level when dosing restarted at next cycle (rash must resolve to \leq Grade 1).
Rash = Grade 4 or Blistering	Discontinue pomalidomide dose and discontinue patient from study.
Constipation \geq Grade 3	Hold pomalidomide dose for remainder of cycle. Initiate bowel regimen. Decrease pomalidomide by one dose level when dosing restarted at next cycle (constipation must resolve to \leq Grade 2).
VTE \geq Grade 3	Hold pomalidomide dose for remainder of cycle. Initiate anti-coagulation treatment. Maintain pomalidomide dose level when dosing restarted at next cycle at discretion of treating physician.
Hypo/hyperthyroidism \geq Grade 2	Hold dose for remainder of cycle. Initiate appropriate medical therapy. Maintain dose level when dosing restarted at next cycle at discretion of treating physician.
Peripheral Neuropathy = Grade 3	Hold pomalidomide dose for remainder of cycle. Decrease pomalidomide by one dose level when dosing restarted at next cycle (neuropathy must resolve to \leq Grade 1).
Peripheral Neuropathy = Grade 4	Discontinue pomalidomide and discontinue patient from study.

For all other \geq Grade 3 pomalidomide-related AEs, hold treatment and restart treatment at 1 mg less than the previous dose when toxicity has resolved to \leq Grade 2 at the discretion of the Investigator.

Instructions for Initiating a New Pomalidomide Cycle

To initiate a new cycle of pomalidomide, ANC must be $\geq 500/\mu\text{L}$ in the US and Canada and $\geq 1,000/\mu\text{L}$ in the EU, the platelet count must be $\geq 50,000/\mu\text{L}$, and non-hematologic AEs must have recovered as outlined in Table 7.

If recovery from toxicities is prolonged beyond 14 days, then the dose of pomalidomide or dexamethasone will be decreased by one dose level.

If the treatment has been interrupted and the next cycle is delayed beyond 29 days after Day 1 of the prior cycle, then Day 1 of the next cycle will be defined as the first day that the treatment is resumed.

5.2.8.3. Dexamethasone

Toxicities considered to be related to dexamethasone are to be managed as shown in Table 8.

Table 8 Dexamethasone Dose Modifications

Category	Toxicity	Grade	Dose Change
Gastrointestinal	Dyspepsia, gastric or duodenal ulcer, or gastritis	Grade 1-2 (requiring medical management)	Treat with H ₂ blockers, sucralfate, omeprazole, or other comparable medications (i.e. proton pump inhibitors). If symptoms persist despite treatment, decrease the dexamethasone dose by 1 level.
		≥Grade 3 (requiring hospitalization or surgery)	Interrupt dexamethasone until symptoms are adequately controlled. Thereafter, resume dexamethasone reduced by one level with concomitant H ₂ blockers, sucralfate, or omeprazole. If symptoms persist despite above measures, permanently discontinue dexamethasone.
	Acute pancreatitis	≥Grade 3	Permanently discontinue dexamethasone.
Cardiovascular	Edema	≥ Grade 3 (limiting function and unresponsive to therapy or anasarca)	Treat with diuretics as needed and decrease dexamethasone by one level. If edema persists despite above measures, decrease by another level. If symptoms persist despite a second reduction, discontinue dexamethasone.
Neurology	Confusion or mood alteration	≥ Grade 2 (interfering with function ± interfering with activities of daily living [ADLs])	Interrupt dexamethasone for up to 2 weeks until symptoms resolve. If symptoms resolve, restart dexamethasone at dose decreased by one level. If symptoms persist despite above measures, then permanently discontinue dexamethasone.
Musculoskeletal	Muscle weakness	≥ Grade 2 (symptomatic and interfering with function ± interfering with ADLs)	Decrease dexamethasone dose by one level. If symptoms persist despite a dose reduction, decrease by another level. If symptoms persist despite above measures, permanently discontinue dexamethasone.
Metabolic	Hyperglycemia	≥ Grade 3	Administer insulin or oral hypoglycemics as needed. If hyperglycemia is not controlled despite treatment, decrease dexamethasone by one level until levels are satisfactory.

The dexamethasone dose reduction steps are summarized in Table 9 and Table 10.

Table 9 Dose Reduction Steps for Dexamethasone (≤ 75 years of age)

Dose Level	Dose (Days 1, 8, 15, and 22)
Starting Dose	40 mg
Dose Level -1	20 mg
Dose Level -2	10 mg

Note: Dexamethasone should be discontinued if patient is unable to tolerate 10 mg dose. Patients may continue on ACY-1215 and pomalidomide until PD.

Table 10 Dose Reduction Steps for Dexamethasone (> 75 years of age)

Dose Level	Dose (Days 1, 8, 15, and 22)
Starting Dose	20 mg
Dose Level -1	12 mg
Dose Level -2	8 mg

Note: Dexamethasone should be discontinued if patient is unable to tolerate 8 mg dose. Patients may continue on ACY-1215 and pomalidomide until PD.

5.3. Blinding, Packaging, and Labeling

5.3.1. Blinding and Breaking the Blind

This is single arm open label study; blinding methods are not applicable.

5.3.2. Packaging and Labeling

As stated previously, ACY-1215 will be supplied by the Sponsor as a liquid (12 mg/ml) for PO administration in 20 mL glass vials. Additional storage conditions and dose preparation instructions will be provided in detail within the Pharmacy Manual.

The label attached to each vial contains the appropriate information, including product name and amount, lot number, directions for storage, date of manufacture, name of Sponsor, and the region-specific regulatory information.

Study drug labels will not contain any statement that is false or misleading in any manner or represent that the study drug is safe or effective for the purposes for which it is being investigated.

Pomalidomide will be provided at 4, 3, 2, and 1 mg for PO administration. Pomalidomide will be dispensed to patients for the duration of their participation in this study at no charge to them or their insurance providers, through the region-specific POMALYST REMSTM or RevAid® program (see Appendix 9.3 and Appendix 9.4, respectively). Pomalidomide capsules are to be stored, per the package insert [51, 58].

Dexamethasone will be packaged and labeled by the manufacturers according to their standard practices.

5.4. Assessment of Treatment Compliance

5.4.1. ACY-1215

Study center pharmacy personnel will prepare individual patient doses to be administered either during scheduled study center visits or by the patient at home.

On ACY-1215 administration days that coincide with study center visits, the ACY-1215 dose prepared by pharmacy personnel will be ingested by the patient at the study center. Prior to leaving the study center, the required number of doses of ACY-1215 prepared by pharmacy personnel will be dispensed to patients for ingestion at home on non-clinic dosing days.

Each time ACY-1215 is dispensed to a patient, study personnel will record the date dispensed, amount dispensed, and the recorder's initials. When the patient returns used and unused study drug containers, study personnel are to record the date returned, amount returned, the recorder's initials, and any comments. A diary will be provided to patients on C1D1 in order to document the date and time of each ACY-1215 dose for all treatment cycles. Following Cycle 1, the Investigator will confirm treatment compliance with the patient at each visit.

